4.5.2 Health-Related Quality-of-Life (HRQoL) Endpoint

The Health Utilities Index (HUI) score and VAS score at each assessment and change from baseline will be calculated from the EQ-5D-5L. In addition, the number of patients who report a clinically meaningful change from baseline to Week 24 on the HUI and VAS will be reported. A meaningful change in the VAS is 7 points and for the HUI it is 0.7 points ([Walters et al. 2005](#); [Pickard et al. 2007](#)).

The Haem-A-QoL, and Haemo-QoL-SF will be analyzed descriptively for each individual subscale and in overall score. Summaries of change from baseline will be provided with 95% CIs. In addition, the proportion of patients reporting a clinically meaningful change from baseline to Week 24 on the physical health and total scores will be reported. A meaningful change on the physical health scale is 10 points and for the total score it is 7 points ([Wyrwich et al. 2015](#)).

The proportion of patients preferring either emicizumab or previous hemophilia treatment regimen will be calculated and presented with 95% CIs based on the patient preference questionnaire. The proportion of patients selecting each reason for their preference and the top three preferred reasons affecting the patient preference will also be summarized.

The number of days away from school/work and days hospitalized will be analyzed using descriptive statistics and 95% CIs.

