2.2 EXPANSION PHASE

2.2.1 Efficacy Objectives

The efficacy objectives are as follows:

- To evaluate the efficacy of prophylactic emicizumab in maintaining adequate control of bleeding
- To evaluate the clinical effect of prophylactic emicizumab on the number of joint bleeds over time
- To evaluate the clinical effect of prophylactic emicizumab on the number of target joint bleeds over time (target joints are defined as joints with ≥ 3 bleeds occurring in the same joint over the last 24 weeks prior to study entry)
- To evaluate the clinical effect of prophylactic emicizumab on the number of all bleeds (i.e., those treated and untreated with coagulation factors) over time
- To evaluate the clinical effect of prophylactic emicizumab on the number of spontaneous bleeds over time (spontaneous bleed rate)

- To evaluate the HRQoL of patients according to Haem-A-QoL ($\geq 18y$) or Haemo-QoL_SF (ages 12–17) scores after 24 weeks
- To evaluate the health status of patients according to EuroQoL 5-Dimension, 5-Level Questionnaire (EQ-5D-5L) scores after 24 weeks
- To assess preference for emicizumab regimen compared with previous regimen used
- To assess the number of days away from school/work
- To assess the number of days hospitalized

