The EQ-5D-5L (see [Appendix 7](#)), is a self-reported health status questionnaire that consists of six questions used to calculate a health utility score for use in health economic analysis (EuroQol Group 1990; Brooks 1996; Herdman et al. 2011; Janssen et al. 2013). There are two components to the EQ-5D-5L: a five-item health state profile that assesses mobility, self-care, usual activities, pain/discomfort, and anxiety/depression, as well as a visual analogue scale (VAS) that measures health state. Published weighting systems allow for creation of a single summary score. Overall scores range from 0 to 1, with low scores representing a higher level of dysfunction. The EQ-5D-5L will be utilized in this study for economic modeling.

Missed Days of School or Work

Patients will also be asked to document the number of days of school or work missed in the previous 4 weeks at the timepoints outlined in the schedule of assessments (see [Appendix 1](#)).

Patient Preference

Patient preference will be assessed through the Preference Survey, which asks patients to report which treatment they would prefer to continue to receive after having been treated with IV FVIII or bypassing agents (episodic or prophylaxis) prior to study entry and SC emicizumab during the study. Patients who express a preference are then asked to identify which reasons may have influenced their decision and indicate the top three reasons for their choice. Patients will complete this questionnaire at Week 17 on emicizumab.

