Appendix 7 EQ-5D-5L (United Kingdom/English) (cont.)

- We would like to know how good or bad your health is TODAY.
- This scale is numbered from 0 to 100.
- 100 means the best health you can imagine.
0 means the worst health you can imagine.
- Mark an X on the scale to indicate how your health is TODAY.
- Now, please write the number you marked on the scale in the box below.

YOUR HEALTH TODAY =

The best health
you can imagine

The worst health
you can imagine

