2.3.3 Health-Related Quality-of-Life (HRQoL) Endpoints

The EQ-5D-5L index utility score using the U.K. value set and visual analog scale (VAS) will be evaluated.

Because different measures, Haem-A-QoL and Haemo-QoL-SF, are used for the adult and adolescent patients, respectively, all calculations and analyses will be conducted

separately for these two measures. For either questionnaire, descriptive analyses including summaries and 95% CIs of change from baseline for each individual subscale and the overall score will be performed.

Proportion of patients preferring emicizumab after 17 weeks of treatment will be presented along with ranked reasons for that choice.

Summary statistics of the number of days away from school/work and days hospitalized will be presented. Number of days of missed daycare/school and days hospitalized will be analyzed using descriptive statistics and 95% CIs.

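### The 0.7-point cutoff for meaningful change in the EQ-5D-5L utility is 70% of a 0-to-1 scale, so the planned responder count is likely to be close to zero

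*SAP*

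**What the plan says.** The protocol lists EQ-5D-5L health status among the efficacy objectives of the expansion phase (Protocol 2.2.1): "To evaluate the health status of patients according to EuroQoL 5-Dimension, 5-Level Questionnaire (EQ-5D-5L) scores after 24 weeks".

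SAP 2.3.3 defines what is evaluated: "The EQ-5D-5L index utility score using the U.K. value set and visual analog scale (VAS) will be evaluated". SAP 4.5.2 gives the utility another name: "The Health Utilities Index (HUI) score and VAS score at each assessment and change from baseline will be calculated from the EQ-5D-5L".

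SAP 4.5.2 then adds a responder summary, "In addition, the number of patients who report a clinically meaningful change from baseline to Week 24 on the HUI and VAS", and sets its cutoffs: "A meaningful change in the VAS is 7 points and for the HUI it is 0.7 points". Two literature references support these figures; no other reason is given.

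The scales are in the protocol. For the EQ-5D-5L summary score, section 4.5.7 states: "Overall scores range from 0 to 1, with low scores representing a higher level of dysfunction". For the VAS, Appendix 7 states: "This scale is numbered from 0 to 100".

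**The concern.** The two cutoffs stand in one sentence and apply to two scores from the same questionnaire, yet relative to their scales they differ tenfold. A threshold for the smallest change that matters to a patient should not require most of the distance between the worst and best scores. The pattern of 7 and 0.7, on scales of width 100 and 1, looks like a misplaced decimal point.

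Programmed as written, the utility count would probably be empty or nearly so. Printed beside a VAS count whose cutoff is a tenth as large relative to its scale, it could be read as showing no meaningful effect on health status, when it would reflect only the threshold. If the number were instead corrected without comment once the data were in hand, a pre-specified responder definition would have changed in an open-label, single-arm study after results could be seen.

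**Working it through.** **Inputs from the documents**

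- Cutoffs: 0.7 for the utility and 7 for the VAS (SAP 4.5.2).
- Utility scale: 0 to 1 (Protocol 4.5.7).
- VAS scale: 0 to 100 (Protocol Appendix 7).
- Patients: 40 in the expansion cohort (SAP 2.4).

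The plan shows no calculation behind 0.7, so there is no figure to reproduce.

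**Step 1: cutoff as a share of the scale**

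- Utility: 0.7 / (1 − 0) = 70%.
- VAS: 7 / (100 − 0) = 7%.
- Ratio: 70 / 7 = 10.

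**Step 2: who can be counted on a 0-to-1 scale**

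- A gain of 0.7 needs a baseline of at most 1 − 0.7 = 0.30.
- A loss of 0.7 needs a baseline of at least 0 + 0.7 = 0.70.
- A patient starting strictly between 0.30 and 0.70 cannot be counted in either direction. Going from 0.50 to 1.00 is a change of 0.50, below the cutoff.

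Steps 1 and 2 use nothing beyond the stated scales and cutoffs.

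**Step 3: expected count at 0.7**

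The documents give no baseline utility, SD, correlation or expected change, so this step rests on assumptions:

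- SD at each visit: 0.15, 0.20, 0.25, 0.30.
- Baseline-to-Week-24 correlation ρ: 0.3, 0.5, 0.7.
- Mean change m: 0, 0.1, 0.2.

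That makes 4 × 3 × 3 = 36 scenarios. With change D normal with mean m and standard deviation s = SD × √(2(1 − ρ)), the expected count in either direction is

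40 × [P(D ≥ 0.7) + P(D ≤ −0.7)].

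The largest value comes from SD 0.30, ρ 0.3, m 0.2:

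- s = 0.30 × √1.4 = 0.355.
- Gains: 40 × P(Z ≥ (0.7 − 0.2)/0.355) = 40 × P(Z ≥ 1.41) = 3.18.
- Losses: 40 × P(Z ≤ (−0.7 − 0.2)/0.355) = 40 × P(Z ≤ −2.54) = 0.23.
- Total: 3.40 of 40 (from unrounded terms).

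| Expected count at 0.7, of 40 | Value |
|---|---|
| Minimum | 0.0 |
| Median | 0.16 |
| Maximum | 3.4 |
| Scenarios below 1 patient | 30 of 36 |

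**Step 4: keeping scores within 0 and 1**

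The normal model ignores the scale limits. A second check used beta-distributed scores linked by a Gaussian copula, with assumed baseline means of 0.5 to 0.8 (132 feasible scenarios). The median was 0.20 of 40 and the maximum 5.5 of 40, which is 5.5/40 = 14%.

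**Step 5: a cutoff with the same share of scale as the VAS**

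For illustration only, 0.07 in the 36 scenarios of Step 3 gives 21.9 to 35.1 of 40, counting both directions. With mean change zero it still gives 21.9 to 33.7, half gains and half losses.

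**The case against.** **The harm is small.** The count is an addition to summaries of score and change from baseline, which do not use the cutoff. The objective is worded in terms of scores, nothing is tested, and no dosing, safety or bleed decision depends on the count. All of this stands and limits the reach of the point. It does not make the cutoff right.

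**Near zero is an inference.** The documents offer no utility distribution, and the check that respects the scale limits reaches 5.5 of 40 at its extreme. That also stands: the fair statement is that the count is usually below one patient, with a few possible under wide assumptions.

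**The range of the U.K. value set is not given and might extend below 0.** Assume floors of −0.3 and −0.6. The share becomes 0.7/1.3 = 54% and 0.7/1.6 = 44%, still far above 7%. The limit on gains does not move, because it depends on the top of the scale. The limit on losses does: it falls to −0.3 + 0.7 = 0.40 and −0.6 + 0.7 = 0.10, so the zone where neither direction is possible narrows to 0.30–0.40 in the first case and vanishes in the second. That zone therefore depends on the 0-to-1 range in the protocol; the scale mismatch survives either floor.

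**The intended value is unknown, and 0.07 is not self-evidently better.** Two scores need not share the same percentage cutoff, and the cited sources were not available for this review. Step 5 also shows that a small cutoff without a direction counts more than half the patients when there is no average change. Both points stand. They are reasons to go to the sources and to separate improvement from worsening, not reasons to keep 0.7.

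**The HUI label is editorial.** Largely true: the SAP says the score is calculated from the EQ-5D-5L, so a programmer is unlikely to look for another instrument.

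**Conclusion.** The concern holds. The mismatch of 70% against 7% of scale follows directly from the SAP and protocol, and neither document gives another cutoff or explains the gap. Applied literally, the rule records some very large improvements as no meaningful change, so it cannot serve as a definition of clinically meaningful change.

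That the count will probably be close to zero is well supported but conditional on the assumed SDs, correlations and mean changes; it is not a certainty. That 0.07 was intended is plausible and unconfirmed.

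This should be fixed before the analysis, because it is a wrong threshold in a pre-specified count. Its reach is that one descriptive count.

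**What to change.** In SAP 4.5.2:

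1. Check 0.7 against the two references already cited for it, replace it with the value they support, and write the scale range of the utility beside it. Do not insert 0.07 on the strength of the VAS parallel alone.
2. Replace the Health Utilities Index (HUI) label with the name used in SAP 2.3.3, "The EQ-5D-5L index utility score using the U.K. value set", so that one score has one name.
3. Optionally, report improvement and worsening separately. Step 5 of the working shows why this helps once the cutoff is small.

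The cost is a short SAP edit after looking up two references. Data collection and trial conduct do not change.

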4.5.3 Subgroup Analyses

Additional descriptive summaries of both treated bleeds and all bleeds will be computed for various subgroups of the study. The summaries will include subgroup ABR and its 95% CIs. The main pre-specified subgroups are as follows:

- Age: <18, ≥18
- Age: <65, ≥65

- Race: Asian, Black or African American, White, Other
- Hemophilia severity: mild, moderate, severe
- Number of target joints at study entry: no target joint, any target joint
- FVIII Inhibitor status: with FVIII inhibitor, without FVIII inhibitors
- Previous treatment regimen: prior episodic, prior prophylactic
- Number of bleeds in the 24 weeks prior to entry: $<9, \geq 9$ for patients being on prior episodic treatment

Note that due to the likely small sample sizes, subgroup analyses will be highly susceptible to variability and should therefore be interpreted with caution.

Additional region- and/or country-specific analyses may be performed to support regulatory submissions as needed.

4.6 PHARMACOKINETIC ANALYSES

4.6.1 PK Run-In Cohort

PK parameters of emicizumab will be estimated using non-compartmental methods after the first and the sixth injection and include:

- T_{max} : Time to maximum observed plasma concentration
- C_{max} : Maximum observed plasma concentration
- AUC_{τ} : Area under the plasma concentration-time curve over a dosing interval
- AUC_{0-inf} : Area under the plasma concentration-time curve between time zero (predose) extrapolated to infinity (only for the first injection)
- $t_{1/2}$: Apparent terminal half-life
- CL/F and CL_{ss}/F: Apparent Clearance

Concentration data and calculated PK parameters for emicizumab will be presented in individual listings, summary tables (including descriptive statistics: mean, geometric means, medians, ranges, standard deviations, and coefficients of variation) and graphs (including concentration versus time plots on linear and semi-logarithmic scales) as appropriate.

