3.1.1 PK Run-In Part

[figure not shown]
In the PK run-in part, a full PK profile will be measured in the first 6 enrolled patients during the first 4 weeks to characterize the pharmacokinetics of a single SC dose of 6 mg/kg emicizumab in patients with hemophilia A. After the first and second emicizumab administration, an intense PK sampling will occur. A reduced PK sampling schedule will be used to characterize repeated Q4W SC administration from Week 9 to Week 21. After the sixth injection at Week 21, PK sampling frequency will be increased to characterize steady-state pharmacokinetics (see [Appendix 2](#)).

An analysis of the data collected when all 6 patients in the PK run-in cohort have been followed for at least 6 weeks will be performed to assess whether the mean PK profile is as predicted (i.e., \geq lower limit of 95% CI of the predicted mean PK profile) after repeated 6 mg/kg SC administration Q4W. In addition to PK, safety will be assessed in order to establish whether the expansion cohort can be opened. This analysis will be conducted by a Roche internal group of representatives from Clinical Pharmacology, Clinical Science, Clinical Safety, and Statistics; no formal Internal Monitoring Committee (IMC) will be set up.

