3.3.1 Rationale for Emicizumab Dose and Schedule

Phase III dosing regimens have been proposed based on modeling and simulation of the PK and efficacy data from patients participating in Part C of Study ACE001JP and in Study ACE002JP.

[figure not shown]
Single- and multiple-dose pharmacokinetics of emicizumab were characterized in Phase I and Phase II studies at doses up to 1 mg/kg and 3 mg/kg, respectively. After a single dose, the emicizumab plasma concentrations peaked 1–2 weeks after dosing. Plasma concentrations subsequently decreased with a mean elimination half-life ($t_{1/2}$) of 28.3–34.4 days, without clear differences among doses. Emicizumab exhibited linear PK, with exposure increasing in proportion to the dose. After multiple doses, in patients with hemophilia A, emicizumab trough plasma concentrations increased in a dose-proportional manner with weekly dosing to achieve a plateau after approximately 12 weeks in groups in which a single loading dose was administered and after approximately 24 weeks in the highest dose group, in which no initial loading dose was administered.

The exposure/response relationship of emicizumab (predicted plasma concentration at the time of bleeding event/bleeding event) was previously characterized with repeated time-to-event (RTTE) modeling. Simulations suggested that a median ABR of 1 is achieved for emicizumab trough plasma concentrations ≥ 16 $\mu\text{g/mL}$ and a median ABR of 0 for emicizumab trough plasma concentrations ≥ 45 $\mu\text{g/mL}$. To achieve this level, once-weekly loading doses of 3 mg/kg for the first 4 weeks followed by QW maintenance doses of 1.5 mg/kg or Q2W maintenance doses of 3 mg/kg have been recommended for the other Phase III studies.

A dose of 6 mg/kg Q4W is equivalent in terms of cumulative dose to the dose levels of 1.5 mg QW or 3 mg/kg Q2W that are being evaluated in the other Phase III studies. Assuming linear PK up to 6 mg/kg, model-based simulations were used to explore whether a Q4W dosing regimen could provide sufficient efficacy. Simulations showed

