- ⁿ Predose (sodium, potassium, glucose, blood urea nitrogen, creatinine, calcium, phosphorus, magnesium, total and direct bilirubin, albumin, alanine aminotransferase, aspartate aminotransferase, and alkaline phosphatase), performed locally. Laboratory assessments completed at the screening visit do not have to be repeated at Week 1 if the period between Screening and Week 1 is 5 days or less and there has been no change in health status as assessed by the investigator. If patients undergo up-titration of their dose after ≥ 24 weeks on emicizumab, an additional blood draw for safety laboratory assessments should be performed within the first 4 weeks after up-titration.
- ^o Female patients with childbearing potential will be required to have a negative serum pregnancy test result at Screening and up to 7 days prior to enrollment (Day – 7 to Day – 1). If applicable, during the study, urine pregnancy tests will be performed at the scheduled visits.
- ^p 6 mg/kg Q4W emicizumab.
- ^q Bleed information (start date and time, reason, type, location, and associated symptoms of each bleed) and medication for bleeds (breakthrough bleeds) should be reported by the patient via an electronic handheld device when a bleed occurs or at least on a weekly basis (retrospective reporting for last 7 days). If the patient discontinues study treatment, bleed and bleed medication data should be provided by the patient until the safety follow-up visit (24 weeks after last study drug administration). Emicizumab doses should be recorded by the patient in the bleed/medication questionnaire starting from Day 1.
- ^r Investigator review of bleed information.

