- ^b During the first 8 weeks, PK sampling will occur at the following timepoints: Week 1 (predose Day 1; 8 hours post-injection on Day 1; then Day 3, Day 5), Week 2 (Day 8, Day 11), Week 3 (Day 15, Day 18), Week 4 (Day 22), Week 5 (Day 29 predose), Week 6 (Day 36), Week 7 (Day 43), and Week 8 (Day 50). A reduced PK sampling schedule will follow to characterize repeated Q4W SC administration from Week 9 to Week 25. From Week 9 to Week 21, patient will have PK blood samples taken at Week 9 (Day 57), Week 13 (Day 85), Week 17 (Day 113), and Week 21 (Day 141). From Week 9 to Week 21, additionally the patient will return once between two emicizumab administrations for a blood sample to be drawn for PK analysis; patients can decide whether this sampling will be 1, 2, or 3 weeks after the latest injection. An individual patient may choose each of the specific intervals (1, 2, or 3 weeks after to the latest injection) at least once. After the sixth injection at Week 21, PK sampling frequency will be increased to characterize steady-state pharmacokinetics, with samples collected at Week 22 (Day 148), Week 23 (Day 155), and Week 24 (Day 162). Another sample will be taken at Week 25 (Day 169) followed by PK assessments every 12 weeks until study completion.
- ^c 8 hours postdose on Day 1.
- ^d Emicizumab ADA blood samples may also be drawn to if hypersensitivity event occur or on an unscheduled basis (at the clinical judgment of the investigator) at any time.
- ^e Set 1 = Standard aPTT, modified aPTT, PT, FVIII activity, thrombin generation, FIX antigen, FX antigen, FVIII antigen (baseline only), D-dimer, prothrombin fragment 1.2, vWF antigen (timepoints of Week 1 Day 1, Week 13, Week 25, study completion or ET, safety follow-up visit), fibrinogen (timepoints of Week 1 Day 1, Week 13, Week 25, study completion or ET, safety follow-up visit), and FXIII activity (baseline only).
- ^f PD assessments occurring once between two Q4W emicizumab administrations to be done on the same day the PK sample is taken (see footnote above).
- ^g Set 2 = FVIII activity, D dimer, prothrombin fragment 1.2, standard aPTT, modified aPTT, and PT.
- ^h A sample for inhibitor testing (anti-FVIII antibodies) must be obtained during screening, within 4 weeks prior to enrollment (i.e., before initiation of Week 1, Day 1 assessments). The results must be available before enrollment, and local testing will not replace the central laboratory inhibitor testing performed at Week 1.

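### First-injection AUC0-inf, t1/2 and CL/F by non-compartmental analysis rest on 28 days of data for a drug with a 28–34 day half-life, so over half of AUC0-inf is extrapolated and the slope is imprecise or biased

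*SAP*

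**What the plan says.** SAP 4.6.1 opens its parameter list with "PK parameters of emicizumab will be estimated using non-compartmental methods after the first and the sixth injection and include". The list holds Tmax, Cmax, AUCtau, AUC0-inf, t1/2, CL/F and CLss/F. AUC0-inf is marked "extrapolated to infinity (only for the first injection". Protocol 6.6 has the same list, as do the protocol synopsis and its copy in SAP Appendix 1.

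Protocol 3.1.1 describes the single-dose part: "a full PK profile will be measured in the first 6 enrolled patients during the first 4 weeks". Protocol Appendix 1 gives the run-in dose as "6 mg/kg Q4W emicizumab", so the second injection falls on Day 29. Footnote b of Protocol Appendix 2 sets samples after the first dose at 8 hours and on Days 3, 5, 8, 11, 15 and 18, and the later ones as "Week 4 (Day 22), Week 5 (Day 29 predose), Week 6 (Day 36". The last sample before the second dose is therefore 28 days after the first. After the sixth injection (Week 21), samples are taken at Weeks 22, 23, 24 and 25, again 28 days in all.

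Protocol 3.3.1 puts the peak 1–2 weeks after a single dose and the mean elimination half-life at a range "of 28.3–34.4 days, without clear differences among doses".

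Neither document gives a limit on the extrapolated share of AUC, a rule for choosing the terminal-slope points, or a rule for parameters that cannot be estimated. Population PK modelling appears under the expansion cohort (SAP 4.6.2, Protocol 6.6). It is not named as the source of the run-in half-life or clearance.

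**The concern.** A non-compartmental AUC0-inf is the observed area plus the last concentration divided by the terminal slope. With the usual definitions (the documents give none), t1/2 is ln 2 over the same slope and CL/F is dose over AUC0-inf. All three need a profile that reaches well into the elimination phase. Here the window is about one half-life from dosing, and up to half of it is absorption.

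At stake is the descriptive account of single-dose pharmacokinetics at 6 mg/kg. Protocol 3.3 says the run-in will inform on dose linearity, and Protocol 3.3.1 assumes linearity up to that dose from single-dose data that stop at 1 mg/kg. Means, SDs and CVs of AUC0-inf, CL/F and t1/2 in about six patients would be tabulated without qualification. They could be taken as observed when they are mostly extrapolated.

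**Working it through.** The documents state no extrapolated fraction, so there is no planned figure to reproduce first.

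**Inputs.** t1/2 is 28.3 to 34.4 days and Tmax 7 to 14 days (Protocol 3.3.1). The window is T = 28 days (Appendices 1 and 2). As a cross-check, the contraception criterion equates five half-lives with 24 weeks, or 168/5 = 33.6 days, which is inside the range.

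**Window in half-lives.** From dosing: 28/34.4 = 0.81 to 28/28.3 = 0.99. For the slope:
- Peak at 7 days: the samples from 10 to 28 days post-dose span 18 days, and 18/28.3 = 0.64.
- Peak at 14 days: the samples from 17 to 28 days span 11 days, and 11/34.4 = 0.32.

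**Extrapolated share.** The model (an assumption) is one compartment with first-order absorption. k = ln 2 / t1/2, and ka solves Tmax = ln(ka/k)/(ka − k). The share beyond T is

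[exp(−kT)/k − exp(−ka·T)/ka] / (1/k − 1/ka).

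- t1/2 28.3, Tmax 7: k = 0.0245, ka = 0.436; (20.565 − 0.000)/(40.828 − 2.295) = 53.4%.
- t1/2 28.3, Tmax 14: ka = 0.157; (20.565 − 0.078)/(40.828 − 6.355) = 59.4%.
- t1/2 34.4, Tmax 7: k = 0.0201, ka = 0.470; (28.230 − 0.000)/(49.629 − 2.127) = 59.4%.
- t1/2 34.4, Tmax 14: ka = 0.174; (28.230 − 0.044)/(49.629 − 5.739) = 64.2%.

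With instantaneous absorption the share is exp(−kT): 50.4% at 28.3 days and 56.9% at 34.4 days. With a 7-day peak it drops below half once t1/2 is under about 25.5 days.

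**Slope, peak at 7 days, true t1/2 28.3 days.** A log-linear fit on 10, 14, 17, 21, 24 and 28 days post-dose gives 29.2 days without error. The 5th–95th percentiles of one patient's estimate are about 24–38 days at 5% error and 20–55 days at 10%. Best-fit selection of at least three points after Cmax gives 17–43 and 13–58 days, so the point-selection rule matters. The documents state no residual error; 5% and 10% are assumptions.

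**Slope, peak at 14 days, no error.**

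| Points (days post-dose) | True 28.3 d | True 34.4 d |
|---|---|---|
| 14, 17, 21, 24, 28 | 48.3 d | 55.4 d |
| 17, 21, 24, 28 | 41.4 d | 47.7 d |
| 21, 24, 28 | 36.5 d | 42.3 d |

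Even the last row overstates t1/2, because absorption is not yet over. It also overstates AUC0-inf, by about 15% and 14%.

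These fits use the Day 25 sample (24 days post-dose). It is in the Appendix 2 schedule table but not in footnote b or SAP 2.3.4.

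**Parameters not affected.** First-injection AUCtau is fully observed. Under the same model, sixth-injection AUCtau is 96–98% of its steady-state value. CLss/F would then be about 2–4% high (1/0.98 = 1.02, 1/0.96 = 1.04).

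**The case against.** The strongest reply is that nothing depends on these values. The decision to open the expansion cohort compares the observed mean concentration profile with the lower 95% bound of the predicted one, together with safety (Protocol 3.1.1, SAP 4.10.1). All analyses are descriptive. The same list already holds sound measures of exposure and clearance in AUCtau and CLss/F, and population estimates are planned. Individual listings, ranges and semi-logarithmic plots in about six patients would show an unstable half-life. All of this stands, and it limits the point to reporting.

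A reader might infer more, and the documents do not support it:
- *That the slope cannot be determined at all.* With a peak near 7 days it can usually be computed with little bias; it is imprecise.
- *That the bias with a 14-day peak is always as large as 48 or 55 days.* Those values fit through the peak itself. Later points reduce the bias without removing it.
- *That more than half is extrapolated in every patient.* At 28.3 days with a 7-day peak the margin is thin, and patients with shorter half-lives fall below half. The protocol's simulated steady state also sits a little outside this model: Cmax/Cavg is 78.1/(1570/28) = 1.39, against a ceiling of 1.38 at 28.3 days. At 18–22 days the share would be about 40–45%, which is still large.
- *That dose linearity is left without evidence.* The protocol does not tie that aim to AUC0-inf, and Cmax and AUCtau address it.

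Visible instability in a listing is a weaker safeguard than a rule set in advance, and it does not reveal the bias from slow absorption.

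**Conclusion.** The concern holds for first-injection AUC0-inf, t1/2 and CL/F, and for t1/2 after the sixth injection. The first-injection result of 53–64% extrapolated uses the protocol's own half-life and peak time under a one-compartment model, and needs no assumption about assay error. The precision figures do depend on the assumed 5% or 10% error and on the points fitted. The upward bias with a late peak does not depend on error, but its size does depend on the points. Following the plan as written would therefore give estimates that are mostly extrapolated, and either imprecise or too high. The consequence is confined to descriptive PK reporting. It does not reach the decision to open the expansion cohort or the efficacy conclusions, and Tmax, Cmax, AUCtau and CLss/F are sound.

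**What to change.** In SAP 4.6.1 and Protocol 6.6, and in the synopsis text of both documents, name as the reported non-compartmental results:
- first injection: Tmax, Cmax and AUCtau over 0–28 days;
- sixth injection: Tmax, Cmax, AUCtau and CLss/F.

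Take t1/2 and CL/F from the population PK model already planned, and state that it includes the run-in data.

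If non-compartmental AUC0-inf, t1/2 or CL/F are kept, list the percent extrapolated for each patient, fix the terminal-slope rules in advance (minimum points, span and fit), and leave values above a pre-set extrapolation limit out of the summary statistics. At a limit of 20% (an assumption; the documents set none), at least 98% of simulated first-injection profiles exceed it, so this option would leave little beyond listings. Reaching 20% would take about 68–86 days of single-dose sampling, which the Day 29 dose rules out.

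Also reconcile the Day 25 sample between the Appendix 2 table, its footnote b and SAP 2.3.4.

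The cost is up to three descriptive parameters dropped or flagged, SAP wording now, and protocol wording at the next amendment, with the approvals that Protocol 9.6 requires. No new samples are needed.
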